7.3. Clinical Laboratory Analyses

Laboratory results will be included in the reporting of this study for hematology, coagulation, clinical chemistry, and urinalysis.

Protocol-specified clinical laboratory tests will be summarized using descriptive statistics. The statistics will be presented for each scheduled assessment during the study and change from baseline to each scheduled assessment. Presentations will use SI Units, as provided by the labs or converted from values in other units. Clinical laboratory data collected during unscheduled visits of study conduct that were not required per protocol, such as for special testing to evaluate an AE, will be listed and not summarized.

Based upon laboratory normal ranges, the laboratory test results will be categorized according to the normal range as low (below the lower limit), normal (within the normal range) and high (above the upper limit). Summary statistics for change from baseline based on PCI will also be tabulated. The details of the planned displays are in Appendix 11: List of Data Displays.

7.4. ECG Evaluations

The following ECG parameters will be reported for each study part: PR, QRS, QT, QTc, QTcF and HR (bpm). Replicate quantitative values taken per time point will be averaged for all analysis and reporting. Summary statistics for change from baseline will also be tabulated.

Overall assessment of ECG (Investigator's judgment) will be recorded as follows:

- Normal
- Abnormal, Not Clinically Significant
- Abnormal, Clinically Significant

7.5. Telemetry Evaluations

Overall assessment of Telemetry (Investigator's judgment) will be recorded as follows:

Normal

- Abnormal, Not Clinically Significant
- Abnormal, Clinically Significant

All measurements will be listed.

7.6. Spirometry Evaluations

The following parameters will be reported for each timepoint: FEV1 and FVC. The maximum of the measurements will be calculated. All measurements will be listed.

% Predicted Normal FEV1 = (Max FEV1/Predicted Normal FEV1)x100

% Predicted FVC = (Max FVC/Predicted Normal FVC)x100

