2.2. Study Objective(s) and Endpoint(s)

| Objectives | | En | Endpoints | |
|------------|---|----|---|--|
| Pri | Primary Objectives | | Primary Endpoints | |
| • | To investigate the safety and tolerability of CCI15106-IP following single and repeat escalating doses in healthy participants and participants with moderate COPD. | • | Adverse events (AEs), clinical laboratory, electrocardiogram (ECG), telemetry, spirometry, and vital signs assessments. | |
| • | To determine systemic PK of CCI15106 following single and repeat escalating doses of CCI15106-IP in healthy participants and participants with moderate COPD. | • | Derived systemic PK parameters of CCI15106: Single dose: area under the curve (AUC) from time zero to the time of last quantifiable concentration (AUC[0-last]), concentration at maximum (Cmax), time of maximum concentration (tmax), AUC from time zero to infinity (AUC[0- ∞]) elimination half-life (t1/2), clearance (CL/F), as data permit. Repeat dose: AUC from time zero to end of dosing interval (AUC[0- τ]) (τ =12 hours [h] for twice daily dose regimen), Cmax, tmax, elimination half-life (t1/2) as data permit. | |
| • | To evaluate potential inhalation exposure of bystanders to airborne | • | Concentration of CCI15106 in plasma of bystanders 15- 20 minutes (min) after dosing (at predicted tmax) and | |

| Objectives | Endpoints |
|---|--|
| CCI15106 during self-administered dosing of participants. | amount of CCI15106 accumulated on filters fitted on bystander over 15 min after dosing. |
| To evaluate the distribution and persistence of airborne CCI15106 in room air post-dosing. | Amount of CC15106 in room air assessed by measuring amount of CCI15106 accumulated over 20 and 60 min intervals during and immediately post-dosing on filters fitted on stationary pumps placed in the room. |
| Secondary Objectives | Secondary Endpoints |
| To determine the concentration of CCI15106 in the lung of healthy participants and participants with moderate COPD following repeat dosing of CCI15106-IP. | Concentrations of CCI15106 in lung epithelial lining fluid (ELF) assessed by bronchoalveolar lavage (BAL). |
| To investigate the performance of the Monodose RS01 device for the administration of CCI15106-IP in healthy participants and participants with moderate COPD. | Device safety and performance parameters, including medical device incidents reporting, as well as systemic PK and lung CCI15106 concentrations. |

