5.2. Baseline Definitions

5.2.1. Baseline Definitions

For all endpoints (except as noted in baseline definitions) the baseline value will be the latest pre-dose assessment.

For tabulated safety summaries, only the scheduled assessments will be included in the summary tables.

| Parameter | Study Assessn | Study Assessments Considered as Baseline | | | | | | | | | |
|----------------------------------|---------------|--|----------------------|------------------|--|--|--|--|--|--|--|
| | Screening | Day -1 | Day 1 (Pre- Dose) | in Data Display | | | | | | | |
| Safety | | | | | | | | | | | |
| 12 Lead ECG & Vital Signs | Х | - | Х | Day 1 (Pre-Dose) | | | | | | | |
| Spirometry | Х | - | X | Day 1 (Pre-Dose) | | | | | | | |
| Haematology/Chemistry/Urinalysis | Х | X | - | Day - 1 | | | | | | | |
| Telemetry | - | - | X | Day 1 (Pre-Dose) | | | | | | | |

NOTES:

 Unless otherwise stated, the mean of replicate assessments at any given time point will be used as the value for that time point.

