11.2. Appendix 2: Schedule of Activities

11.2.1. Protocol Defined Schedule of Events

Screening and follow-up procedures for all cohorts

| Procedure | Screening, ≤ 30 days before D1 for Part 1 or ≤ 45 days before D1 for Part 21 | Follow up 30±2 days after the last dosing day | Notes |
|---|--|---|--|
| Informed consent | Х | | Screening assessments can be performed over multiple screening visits |
| Inclusion and exclusion criteria | X | | If test otherwise performed within 3 months prior to first dose of study treatment, testing |
| Demography | X | | at screening is not required |
| Full physical examination including height and weight, oral examination | Х | | To be drawn fasting (for at least 8 h) To be administered to participants with COPD only, 15-30 minutes prior to spirometry |
| Brief physical examination, oral examination | | Х | To be done at screening for participants with COPD only, following salbutamol dosing To be performed in the bronchoalveolar lavage (BAL) cohorts only to confirm participant |
| Medical history (includes substance usage and Family history of premature CV disease) | х | | eligibility 7. To be performed in the BAL cohorts only to confirm participant eligibility. Can be done pre-dose on Day -1 instead, if required |
| Substance testing (drugs, alcohol) | X | | |
| Assessment of child-bearing potential for females | Х | | |
| Serum pregnancy test in women | X | X | |
| Human immunodeficiency virus (HIV), Hepatitis B (Hep B) and Hepatitis C (Hep C) screen ² | Х | | |
| Haematology, clinical chemistry and urinalysis (include liver chemistries) ³ | Х | X | |
| Salbutamol administration ⁴ | X | | |
| Spirometry ⁵ | X | | |
| 12-lead ECG and vital signs | Х | X | |
| Coagulation parameters ⁶ | X | | |
| Capillary pCO ₂ ⁷ | X | | |
| PK blood sample | | X | |
| AE review | | X | |
| SAE review | X | X | |
| Concomitant medication review | X | X | |

Schedule for Cohort A Part 1

| Procedure | | | | | | | | | | Tre | eatmer | nt Peri | od, Da | ıys | | | | | | | | | |
|---|----|------------------|-----------------|------------|---|---|----|----|-----------------------|----------------|----------------|----------------|--------|-----|----------------|----------------|----|----|----------------|----|----|--------------|----|
| | -1 | 11 | 2 | 31 | 4 | 5 | 6 | 7 | 8 | 9 | 10 | 11 | 12 | 13 | 14 | 15 | 16 | 17 | 18 | 19 | 20 | 21 | 22 |
| Inclusion and exclusion criteria | Х | | | | | | | | | | | | | | | | | | | | | | |

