| 3.27. | Bystander Safety (Part 1, Cohort C) | LB1 | Summary of Haematology Changes from Baseline by Visit – Bystander | Only for Cohort C, Part 1. | SAC | | | |
| 3.28. | Safety | LB17 | Summary of Hematology Values by Potential Clinical Importance – Part 1 | This will not include Cohort C, Part 1. | SAC | | | |
| 3.29. | Safety | LB17 | Summary of Hematology Values by Potential Clinical Importance – Part 2 | | SAC | | | |
| 3.30. | Bystander Safety (Part 1, Cohort C) | LB17 | Summary of Hematology Values by Potential Clinical Importance – Bystander | Only for Cohort C, Part 1. | SAC | | | |

| Safety: | Safety: Tables | | | | | | |
|---------|---|-------------------------|---|---|---------------------------|--|--|
| No. | Population | IDSL / Example Shell | Title | Programming Notes | Deliverable [Priority] | | |
| Labora | tory: Coagulati | on | | | | | |
| 3.31. | Safety | LB1 | Summary of Coagulation Changes from Baseline by Visit – Part 1 | Only for Cohorts B, Part 1. | SAC | | |
| 3.32. | Safety | LB1 | Summary of Coagulation Changes from Baseline by Visit – Part 2 | Only for Cohorts B, Part 2. | SAC | | |
| Teleme | try | | | | | | |
| 3.33. | Safety | Non-standard SAFE_T2 | Summary of Telemetry Findings – Part 1 | This will not include Cohort C, Part 1. | SAC | | |
| 3.34. | Safety | Non-standard SAFE_T2 | Summary of Telemetry Findings – Part 2 | | SAC | | |
| Spirom | etry | | | | | | |
| 3.35. | Safety | Non-standard SAFE_T3 | Summary of Spirometry Data – Part 1 | This will not include Cohort C, Part 1. | SAC | | |
| 3.36. | Safety | Non-standard SAFE_T3 | Summary of Spirometry Data – Part 2 | | SAC | | |
| ECG | | | | | | | |
| 3.37. | Safety | EG1 | Summary of ECG Findings by Visit – Part 1 | This will not include Cohort C, Part 1. | SAC | | |
| 3.38. | Safety | EG1 | Summary of ECG Findings by Visit – Part 2 | | SAC | | |
| 3.39. | Bystander Safety (Part 1, Cohort C) | EG1 | Summary of ECG Findings by Visit – Bystander | Only for Cohort C, Part 1. | SAC | | |
| 3.40. | Safety | EG2 | Summary of Change from Baseline in ECG Values by Visit – Part 1 | This will not include Cohort C, Part 1. | SAC | | |

| Safety: | Tables | | | | |
|----------|---|-------------------------|---|--|---------------------------|
| No. | Population | IDSL / Example Shell | Title | Programming Notes | Deliverable [Priority] |
| 3.41. | Safety | EG2 | Summary of Change from Baseline in ECG Values by Visit – Part 2 | | SAC |

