11.11. Appendix 11: Example Mock Shells for Data Displays

Example SAFE_T1
Protocol: 205822
Population: Safety

Page 1 of 2

Table 1.61
Summary of Demographic Characteristics - Part 1

| | | Cohort B (N=12) | Placebo (N=4) |
|---|----------|-----------------|------------------|
| Sex | | | |
| n | 6 | 12 | 4 |
| Male | 6 (100%) | 12 (100%) | 4 (100%) |
| Female | 0 | 0 | 0 |
| Age (y) | | | |
| n | 6 | 12 | 4 |
| Mean | 39.8 | 35.4 | 43.3 |
| SD | 9.75 | 11.18 | 9.54 |
| Median | 40.0 | 31.0 | 44.0 |
| Min. | 25 | 25 | 32 |
| Max. | 52 | 57 | 53 |
| Ethnicity | | | |
| n | 6 | 12 | 4 |
| HISPANIC OR LATINO | 0 | 1 (8%) | 0 |
| NOT HISPANIC OR LATINO | 6 (100%) | 11 (92%) | 4 (100%) |
| Race | | | |
| n | 6 | 12 | 4 |
| WHITE - WHITE/CAUCASIAN/EUROPEAN HERITAGE | 5 (83%) | 9 (75%) | 4 (100%) |
| AFRICAN AMERICAN/AFRICAN HERITAGE | 1 (17%) | 2 (17%) | 0 |
| Multiple . | 0 | 1 (8%) | 0 |

.

Example SAFE_T2
Protocol: 205822

Population: Safety

Table X
Summary of Telemetry Findings - Part 1

| | _ | ohort A (N=157) | Cohort B (N=160) | | | Placebo (N=160) |
|--------------------------------------|-----|--------------------|------------------|-------|-----|--------------------|
| Time Period 1 | | | | | | |
| n | 156 | | 160 | | 160 | |
| Normal | 81 | (52%) | 90 | (56%) | 90 | (56%) |
| Abnormal, not clinically significant | 75 | (48%) | 69 | (43%) | 69 | (43%) |
| Abnormal, clinically significant | 0 | | 1 | (<1%) | 1 | (<1%) |
| Time Period 2 | | | | | | |
| n | 117 | | 123 | | 123 | |
| Normal | 50 | (43%) | 67 | (54%) | 67 | (54%) |
| Abnormal, not clinically significant | 64 | (55%) | 55 | (45%) | 55 | (45%) |
| Abnormal, clinically significant | 2 | (2%) | 1 | (<1%) | 1 | (<1%) |

•

.

.

Example SAFE_T3
Protocol: 205822

Population: Safety

Table X Summary of Spirometry Results - Part 1

| | CCI15106 | CCI15106 | CCI15106 | Placebo |
|-----------------|----------|----------|----------|---------|
| | 60mg SD | 120mg SD | 30mg BID | |
| | (N=157) | (N=160) | (N=160) | (N=160) |
| Time Period 1 | | | | |
| n | 156 | 160 | | 160 |
| %Predicted FEV1 | 52% | 56% | | 56% |
| %Predicted FVC | 55% | 45% | | 45% |
| Time Period 2 | | | | |
| n | 117 | 123 | | 123 |
| %Predicted FEV1 | 52% | 56% | | 56% |
| %Predicted FVC | 55% | 45% | | 45% |
| | | | | |
| • | | | | |
| • | | | | |
| • | | | | |
| • | | | | |

[%] Predicted FEV1 = (Max FEV1/Predicted Normal FEV1)x100

[%] Predicted FVC = (Max FVC/Predicted Normal FVC)x100

Example SAFE_T4
Protocol: 205822

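### Spirometry has a defined Day 1 pre-dose baseline, but no planned display reports change from it

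*SAP*

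**What the plan says.** Section 2.2 lists the primary safety endpoints as "Adverse events (AEs), clinical laboratory, electrocardiogram (ECG), telemetry, spirometry, and vital signs assessments". The product is inhaled: a secondary objective is "To investigate the performance of the Monodose RS01 device for the administration of CCI15106-IP".

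Section 7.6 is the whole spirometry analysis text. It states "The following parameters will be reported for each timepoint: FEV1 and FVC. The maximum of the measurements will be calculated", promises a listing of all measurements, and defines percent-predicted values for FEV1 and FVC, the latter as "Predicted FVC = (Max FVC/Predicted Normal FVC)x100". Change is not mentioned.

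Section 5.2.1 gives the general rule "For all endpoints (except as noted in baseline definitions) the baseline value will be the latest pre-dose assessment". Its table marks both screening and Day 1 pre-dose for spirometry, and names Day 1 pre-dose as the baseline for display. Section 5.2.2 defines absolute and percent change from baseline.

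The only spirometry tables in Section 11.10.5 are 3.35, "Summary of Spirometry Data – Part 1", and its Part 2 counterpart 3.36. Both point to shell SAFE_T3 in Appendix 11, titled "Summary of Spirometry Results - Part 1".

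**The concern.** The tolerability question that spirometry answers for an inhaled product is whether a participant's lung function falls after dosing, and whether it drifts down over repeated dosing. Both compare participants with themselves. The schedule collects the data for both comparisons and the SAP defines the baseline, but the planned outputs stop at the level at each time.

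What is at stake is how well a primary safety component is described. As planned, the report would have no tabulated SD of change, no minimum or maximum change, and no largest fall per participant. Appendix 7 has no range of potential clinical importance for spirometry, so no categorical table fills the gap.

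**Working it through.** The SAP states no sample size, power or SD for spirometry, so there is no figure to reproduce. The main check is a trace of every place that governs the spirometry output.

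| Place in SAP | Content | Change from pre-dose? |
|---|---|---|
| Section 7.6 | FEV1, FVC, maximum reading, percent predicted, listing | No |
| Table 3 | Absolute summary table and absolute listing marked | All four change cells empty |
| Tables 3.35, 3.36 | One summary per part, shell SAFE_T3 | No |
| Shell SAFE_T3 | n, percent-predicted FEV1, percent-predicted FVC, one figure per cell | No |
| Shell SAFE_L1 | Readings 1 to 3, highest reading, percent predicted | No change column |

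Table 3 alone would not settle the matter. It also leaves the coagulation change cells empty, although Tables 3.31 and 3.32 are change tables. For spirometry, the display list and both shells confirm the omission.

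**Contrast.** Change-from-baseline tables exist for chemistry (3.19 to 3.21), haematology (3.25 to 3.27), coagulation (3.31, 3.32), ECG (3.40 to 3.42) and vital signs (3.52 to 3.54). Coagulation has them although the schedule in Section 11.2.1 takes it only at screening.

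**Paired data.** Section 11.2.1 schedules a pre-dose reading on every spirometry day:
- Single-dose days: pre-dose, then 0.25, 0.5, 1 and 4 h.
- Part 1 Cohort A, Days 6 and 19: the same times.
- Part 1 Cohort A, Days 8, 11 and 16: pre-dose and 4 h only.
- Other repeat-dose cohorts, Days 1 and 14: pre-dose, 0.25 h (COPD only), 0.5, 1 and 4 h.
- Other repeat-dose cohorts, Days 3, 6 and 11: pre-dose and 4 h only.

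**What can be recovered from the planned tables.** If the same participants contribute at both times, post-dose mean minus pre-dose mean equals the mean change. The SD, minimum and maximum of the individual changes cannot be recovered from summaries at separate times.

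**Illustration of precision (assumed inputs).** With equal SDs before and after dosing and correlation rho, SD(change) = SD × sqrt(2(1 − rho)).
- rho 0.80: sqrt(0.40) = 0.63
- rho 0.90: sqrt(0.20) = 0.45
- rho 0.95: sqrt(0.10) = 0.32

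The 95% half-width of a mean is t(0.975, n − 1) × SD / sqrt(n). The group sizes of 6 and 12 appear only in mock shells. For an assumed between-participant SD of 15 percentage points:

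| n | Absolute mean | Change, rho 0.80 | Change, rho 0.90 | Change, rho 0.95 |
|---|---|---|---|---|
| 6 | 15.7 | 10.0 | 7.0 | 5.0 |
| 12 | 9.5 | 6.0 | 4.3 | 3.0 |

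Over assumed SDs of 10 to 20, the absolute half-width runs from 10.5 to 21.0 at n = 6 and from 6.4 to 12.7 at n = 12. The change half-widths scale by the same three ratios.

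**Why mean change alone is not enough.** Suppose the SD is 10 and one participant falls by 10 points.
- n = 12: either mean moves by 10/12 = 0.8. The SE is 10/sqrt(12) = 2.9 for the absolute mean, and 1.8, 1.3 or 0.9 for the mean change.
- n = 6: either mean moves by 10/6 = 1.7. The SE is 4.1 for the absolute mean, and 2.6, 1.8 or 1.3 for the mean change.

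The shift exceeds one SE only at n = 6 with rho 0.95. A single fall shows up in the minimum change and the per-participant largest fall.

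**The case against.** The strongest reply is that nothing is lost from the record. A reader might infer that a post-inhalation fall would be hidden. The documents do not support that: Section 7.6 lists all measurements, and SAFE_L1 shows the readings and the highest value by participant and visit, so an individual fall can be worked out by hand. This stands, and limits the point to the summaries.

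A reader might also infer from SAFE_T3 that no measure of spread will be given, or that FEV1 and FVC will be summarised only as percent predicted. SAFE_T3 is an example with placeholder figures. Section 7 already requires N, mean, SD, median, minimum and maximum for continuous safety variables, and Section 7.6 has FEV1 and FVC reported at each time. This is a shell out of line with the text. Correcting it would give the spread of levels but still not the spread of changes.

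A third tempting inference is that post-bronchodilator screening values contaminate the baseline, because screening spirometry is "To be done at screening for participants with COPD only, following salbutamol dosing". Section 5.2.1 fixes Day 1 pre-dose for display and takes the latest pre-dose value. Screening could enter only if Day 1 pre-dose were missing, and no planned display currently uses the baseline. It is a fallback risk for new tables and no more.

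Finally, Section 2.4 says that no hypotheses will be tested, so arguments from standard errors carry limited weight. That is fair. The case rests on describing within-participant change, and the precision figures only illustrate it.

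**Conclusion.** The point holds as an internal inconsistency with an inexpensive remedy. The SAP sets a spirometry baseline and a change formula and schedules paired readings for a primary safety component, but no display uses them. The loss is confined to the summaries: the distribution of within-participant changes and the largest fall.

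Its numerical size cannot be fixed from the SAP. The ratio of 0.63 to 0.32 rests on an assumed correlation of 0.80 to 0.95 and equal SDs. The half-widths also rest on an assumed SD and on group sizes taken from mock shells. The direction, a smaller SD for change than for level, holds whenever the correlation exceeds 0.5. Nothing here shows that a safety signal would be missed.

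**What to change.** Amend Section 7.6, Table 3, Tables 3.35 and 3.36, and shells SAFE_T3 and SAFE_L1 as follows.

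1. Summarise absolute and percent change in FEV1 and FVC from the Day 1 pre-dose baseline at each scheduled post-dose time, with n, mean, SD, median, minimum and maximum.
2. Add change from same-day pre-dose on days with paired readings. Day 1 pre-dose follows the existing baseline definition and captures drift over repeat dosing. Same-day pre-dose isolates the acute post-inhalation fall. Neither replaces the other, especially in Part 1 Cohort A, which has several dosing periods.
3. Show each participant's largest post-dose fall by dosing day. The number of post-dose readings differs (one on the 4 h-only days, three or four on the others), and a minimum over more readings tends to be more extreme.
4. Add a change column to SAFE_L1.
5. Redraw SAFE_T3 to carry the descriptive statistics that Section 7 requires.
6. As a minor precaution for the new tables, state that post-salbutamol screening spirometry in COPD participants is not substituted when Day 1 pre-dose is missing.

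Whether to define a notable fall is for the sponsor; none is needed for these displays. The cost is SAP wording, shell revision and some programming. No new data, visit or procedure is required.

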7.7. Vital Signs

The following Vital Signs measurements will be reported for each study part: supine systolic and diastolic blood pressure, pulse rate, respiratory rate and temperature.

For participants undergoing BAL, vital signs will also include oxygen saturation.

Triplicate quantitative values taken per time point will be averaged for all analysis and reporting.

Summary statistics for collected vital signs, change from baseline, and summary of PCI will also be tabulated.

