- 7. To be performed at the following timepoints in the mornings only: pre-dose, and 0.25 (in participants with COPD only), 0.5, 1, 4 h post-dose
- 8. To be performed at the following timepoints in the mornings only: pre-dose and 4 h post-dose

- 9. Telemetry may be performed on Days 11 or 12 instead, not to coincide with the BAL procedure.
- 10. ECG and vital signs to be obtained 2 h after the morning dose
- 11. When BAL is performed, vital signs and ECG will be performed before and after the procedure and oxygen saturation will be measured continuously.
- 12. For cohort with bystanders, BID doses may have ±1.5 h window.
- 13. PK samples on days 1 and 14 will be collected at the following timepoints: pre-dose, 0.25, 0.5, 0.75, 1, 2, 4, 6, 8, 10, 12 h. The evening dose will be given after 12 h post-dose sample is collected. On all other days, PK sample will be collected once, before the morning dose. When BAL is performed, one additional PK sample will be collected after dosing immediately prior to bronchoscopy
- 14. Done once during these four days, as soon as possible (within 1 h) after the first dose of the day
- 15. To be collected immediately before bronchoscopy

Schedule for Cohort C Part 1 (bystanders and air monitoring), to be executed concomitantly with Cohort B Part 1

| Procedure Treatment Period, Days | | | | | | | | | | | | | | | | |
|---|----------------|----------------|---|-----------------------|----|--------------------|-------------------|----------------|----|---|-----------------------|----|----|----|----------------|----|
| | -1 | 1 | 2 | 3 | 4 | 5 | 6 | 7 | 8 | 9 | 10 | 11 | 12 | 13 | 14 | 15 |
| Inclusion and exclusion criteria | X | | | | | | | | | | | | | | | |
| Brief physical examination, oral examination | X | | | | | | | | | | | | | | | Х |
| Substance testing (drugs, alcohol, tobacco) | Х | | | | | | | | | | | | | |] | |
| Serum pregnancy test in women | Х | | | | | | | | | | | | | | | |
| Admittance to clinic | X | | | | | | | | | | | | | | | |
| Discharge | | | | | | | | | | | | | | | | X1 |
| Training ² | X | | | | | | | | | | | | | | | |
| Haematology, clinical chem and urinalysis (include liver chem)3 | X | | | | | | | Χ | | | | | | | | Χ |
| Exposure to dosing | | Χ | Χ | X | Χ | X | X | X | Χ | X | Χ | X | X | X | Χ | |
| PK blood sample | | X ⁴ | | | | | | X ⁴ | | | | | | | X ⁴ | X |
| Stationary pump air monitoring ⁵ | | Χ | | | | | | Χ | | | | | | | Χ | |

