11.5. Appendix 5: Derived and Transformed Data

11.5.1. General

Multiple Measurements at One Analysis Time Point

- Mean of the measurements will be calculated and used in any derivation of summary statistics but if listed, all data will be presented.
- Subjects having both High and Low values for Normal Ranges at any post-baseline visits for safety
 parameters will be counted in both the High and Low categories of "Any visit post-baseline" row of
 related summary tables. This will also be applicable to relevant Potential Clinical Importance summary
 tables.

Study Day

- Calculated as the number of days from randomisation date:
 - Ref Date = Missing
 - → Study Day = Missing
 - Ref Date < Randomisation Date → Study Day = Ref Date Randomisation Date
 - Ref Date ≥ Randomisation Date → Study Day = Ref Date (Randomisation Date) + 1

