11.7.3. Vital Signs

| Vital Sign Parameter | Units | Clinical Concern Range | | |
|--------------------------|-------|------------------------|-------|--|
| (Absolute) | | Lower | Upper | |
| Systolic Blood Pressure | mmHg | < 85 | > 160 | |
| Diastolic Blood Pressure | mmHg | < 45 | > 100 | |
| Heart Rate | bpm | < 40 | > 110 | |

| Vital Sign Parameter | Units | Clinical Concern Range | | |
|--------------------------|-------|------------------------|----------|--|
| (Change from Baseline) | | Decrease | Increase | |
| Systolic Blood Pressure | mmHg | ≥ 40 | ≥ 40 | |
| Diastolic Blood Pressure | mmHg | ≥ 20 | ≥ 20 | |
| Heart Rate | bpm | ≥ 30 | ≥ 30 | |

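### For oxygen saturation at BAL, the plan specifies only averaging and a pre-dose reference, so no summary table is set to show the lowest value or the fall from the pre-procedure reading

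*SAP*

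**What the plan says.** - **SAP 7.7:** "For participants undergoing BAL, vital signs will also include oxygen saturation". The same section averages repeat readings ("Triplicate quantitative values taken per time point will be averaged for all analysis and reporting") and promises summary statistics, change from baseline and a PCI summary for vital signs. It makes no exception for saturation.
- **SAP 11.2.1, repeat-dose schedule, note 11:** "When BAL is performed, vital signs and ECG will be performed before and after the procedure and oxygen saturation will be measured continuously".
- **SAP 5.2.1:** "For all endpoints (except as noted in baseline definitions) the baseline value will be the latest pre-dose assessment". The table there displays the vital-sign baseline as Day 1 pre-dose. A note adds that, unless otherwise stated, "the mean of replicate assessments at any given time point will be used as the value for that time point".
- **SAP 5.2.2:** where baseline is missing, no change is derived.
- **SAP 11.5.1:** "Mean of the measurements will be calculated and used in any derivation of summary statistics but if listed, all data will be presented".
- **SAP 11.7.3:** PCI ranges are given for systolic pressure, diastolic pressure and heart rate only.
- **SAP 11.10:** vital signs and their changes are tabulated by visit (Tables 3.49, 3.50, 3.52 and 3.53) and by PCI (3.55 and 3.56). Listings 62 and 63 give all vital signs. Listings 65 and 66 cover participants with a PCI value.

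**The concern.** Saturation is added to the vital signs specifically for participants who have a bronchoscopy. The question it can answer is how far saturation fell, and from what level just before the procedure. Answering it needs the lowest reading and a pre-procedure reference, and the plan names neither. The rules it does supply suit resting blood pressure at a fixed visit. They average readings and look back to a value taken before the first dose.

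Safety and tolerability is a primary objective (Section 2.2). The BAL takes place within 1 h of the first dose of the day, in healthy participants and in participants with moderate COPD. A short fall in saturation could reflect the procedure, the inhaled product or both. If the tables show only a mean, or no change at all, a reader comparing active with placebo, or Part 1 with Part 2, cannot see it without going through the listings.

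**Working it through.** The plan states no figure on this point, so nothing can be reproduced. The check follows saturation from collection to display.

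1. **Collection.** Note 11 provides a reading before the procedure, a reading after it, and continuous measurement. The data for a pre-procedure reference and a lowest value are thus scheduled, as far as they are entered in the database.

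2. **Reduction to an analysis value.** Three rules could apply, in Sections 5.2.1, 7.7 and 11.5.1. All three are means. Section 7.7 refers to triplicates, and the other two to replicates or multiple measurements at one time point. None is written for a continuous recording and none takes a minimum. A programmer with several saturation values for the BAL time point would find only averaging rules. Elsewhere the plan does depart from the mean: spirometry uses the maximum (Section 7.6), and the ECG category tables use the maximum and the worst change (Tables 3.43 to 3.48).

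3. **Reference for change.** There are two readings of when saturation is taken:
   - *At every vital-sign assessment of BAL participants.* The reference is then the latest pre-dose value, displayed as Day 1 pre-dose. Note 14 allows the BAL once within four days. The schedule grid and note 9 place these at Days 10 to 13. The gap from Day 1 is 10 − 1 = 9 to 13 − 1 = 12 days.
   - *Only around the BAL.* There is then no pre-dose baseline, and Section 5.2.2 sets the change to missing.

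   On both readings the change across the procedure is not derived, although the pre-procedure value is scheduled.

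4. **Flagging.** Section 11.7.3 has no saturation row. Saturation therefore cannot enter Tables 3.55 and 3.56, and cannot by itself place a participant in Listings 65 and 66.

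5. **Summary layout.** The vital-sign tables run by visit, while the BAL may fall on any of four days. Values around the procedure are not aligned to it.

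6. **What remains visible.** Listings 62 and 63 carry the vital signs, and Section 11.5.1 shows every measurement when data are listed. Section 11.4.2 keeps unscheduled readings in listings. A desaturation recorded as an adverse event enters the adverse event tables and listings.

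**The case against.** The strongest reply is that nothing is lost, and much of it stands. A reader might infer from the averaging rules that a desaturation would go unreported. The documents do not support that, given the full listings and the adverse event displays in step 6. The wording in Section 7.7 that averages for all reporting sits uneasily with Section 11.5.1, but the latter speaks directly to listings.

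A reader might also infer that the plan expressly averages the continuous recording. It does not. Section 7.7 names triplicates, and the readings before and after the procedure are separate time points. The gap is that no other rule is given. For the same reason, no worked figure for how much a mean would dilute a fall is offered: it would need invented readings and an assumption about which of them share a time point.

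Nor is it established that saturation is taken only around the BAL. Section 7.7 can be read as covering every vital-sign assessment in these participants, so it cannot be said that a Day 1 baseline is impossible.

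A missing PCI row is not an error in itself. Respiratory rate and temperature have none either, and a saturation category would be a clinical choice for the sponsor. How much of the continuous recording reaches the database is also a matter for the protocol and CRF, which are not at hand.

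None of this supplies a rule for the lowest value or for the change from the pre-procedure reading. That part of the point is unaffected.

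**Conclusion.** The point holds as a gap in the summary tables. Followed as written, the plan derives neither the lowest saturation at BAL nor its fall from the pre-procedure reading, and has no PCI category to flag it. A BAL-related fall may be masked in the tables, or its change may be absent from them, while remaining visible in Listings 62 and 63 or as an adverse event.

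It touches every participant who has a BAL in Cohort B of Parts 1 and 2. The study is descriptive and tests no hypothesis, so no main conclusion is at risk. The correction is worth making because it concerns a primary safety objective and uses readings already scheduled. The conclusion does not depend on whether saturation is taken throughout or only around the BAL. It does assume that at least one pre-procedure value and some values during or after the procedure are entered in the database.

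**What to change.** In Section 7.7:

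- Exempt oxygen saturation from the averaging rule.
- Define its reference as the last reading before bronchoscopy, in place of the pre-dose baseline in Section 5.2.1.
- For participants who undergo BAL, tabulate by part and treatment the pre-BAL value, the lowest recorded value during or after the procedure, and the difference (lowest minus pre-BAL). Use the readings captured in the database, and footnote that the minimum is limited to those.
- State that the PCI summary does not cover saturation unless the sponsor adds a category.

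The existing vital-sign listings suffice, and the other vital signs need no new display. The cost is a few lines of SAP text and one small table per part. If only selected readings from the continuous recording are entered, the tabulated minimum may miss the true lowest point.
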